17.5.4 Controlling the Alpha level for the primary endpoint

The overall alpha level for this study is 5%. According to references 25-27, planning an interim analysis that permits an increase in the sample size as described above does not inflate the type I error.

Doc No: 280CLD	
Rev: 01	Date: 24 May 2021
Page 70 of 103	

Page 70 of 103

Randomization 17.6

After a subject meets the eligibility criteria, he/she will be equally allocated (with a 1:1 ratio) to one of the following treatment groups based on a randomization scheme with randomized blocks' size stratified by center:

- Vibrant capsule administered twice a week
- Placebo capsule administered twice a week

The randomization scheme will be prepared by BioStats using the SAS® (version 9.4.) random number generating procedure.

17.7 **Blinding**

This is a double-blind study. The subjects and evaluators will be blinded to the treatment allocated to each subject.

17.8 Data Analysis Sets

Safety (SA) 17.8.1

The SA analysis set will consist of all subjects randomized. Subjects will be analyzed in the treatment group as treated.

17.8.2 Intent to Treat (ITT)

The ITT analysis set will consist of all subjects randomized. In accordance with the ITT principle, all subjects randomized will be kept in their originally assigned treatment group for analysis. Subjects with no valid post baseline assessment will not be part of the relevant analysis.

Modified Intent to Treat (mITT) 17.8.3

The mITT analysis set will consist of all randomized subjects who met the inclusion criteria of the protocol. In accordance with the ITT principle, all subjects randomized will be kept in their originally assigned treatment group. Subjects with no valid post baseline assessment will not be part of the relevant analysis. Subjects with less than 2 weeks (with at least 5 days per week) of valid diary during the treatment period will be considered as non-evaluable

 Doc No: 280CLD

 Rev: 01
 Date: 24 May 2021

Page 71 of 103

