17.5.1 Procedure

After all the relevant data will be entered into the database, and the database cleaned, a soft lock to the database will be performed. An independent un-blinded statistician (not the study statistician) will perform the assessments described below. At the interim analysis, the data of the evaluable subjects will be analyzed.

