17.5.3 Decision Rules

The purposes of the interim analysis is to re-assess the sample size based on conditional power

The study will either continue to the originally planned sample size if the result is "favorable", stop for futility if the result is "unfavorable", or an increase will be made to the sample size if the result is "promising". These decisions will be made based on the

Page 69 of 103

conditional power (CP), defined as the conditional probability that the result will exceed a critical value at the interim given the observed effect size $\widehat{\delta_1}$ = difference between CSBM success rates active versus placebo at the interim look. Notation:

n1= sample size at interim analysis (40 subjects in each study arm).

n2= original sample size calculated based on assumed effect size (92).

nmax = the highest sample size the company is willing to use, <math>nmax = 250 (including allowance for drop-out).

CPmin=is the calculated minimum CP based on the ratios nmax/n2, n1/n2 and the target study power (80%).

The following are the decision rules for the interim analysis. These depend on the zone into which CP falls at the interim, the calculated CPmin, the maximum sample size designated for the study and the % of the originally planned sample size at which the interim analysis will be performed. Following this principle does not inflate the Type I error.

- 1. If the respective conditional power for each of the primary endpoints is < 25.78or if the difference between the success rate (treatment –placebo) for both primary endpoints is less than 10%, then stop the trial for futility.
- 2. a. If the conditional power for both primary endpoints is 25.78≤ CP < 80% then recalculate the sample size to recover the targeted 80% for both endpoints, the maximum sample size selected will be the larger of the two.
 - b. If the CP of only one of the primary endpoints is $25.78 \le CP \le 80\%$ then recalculate the sample size to recover the targeted 80% for that endpoint alone.
 - In both cases a and b, the maximum sample size for the study will be 250 subjects
- 3. If the respective conditional power for each of the primary endpoints is $\geq 80\%$ then continue to the originally planned sample size. Note that the interim analysis will be conducted on both the ITT and mITT analysis sets, and the study will be stopped due to futility only if the interim effects in both populations fall below the threshold.

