17.8.5 Statistical Analysis of Analysis Sets

The SA analysis set will serve as the main set for safety assessments.

The mITT analysis set will serve as the main set for efficacy assessments.

The efficacy assessment will be presented on the ITT and PP analysis sets.

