17.9.8 Handling of Missing Data

Subjects with less than 6 weeks of diary data will be considered as failures for the CSBM and SBM success rates, as the primary imputation method for missing data.

Additional sensitivity analysis of the primary end-point will be performed to assess the impact of missing data on the study outcome using possible imputation methods for binary data:

- Multiple imputation for binary data.
- Observed Data: Use only subjects with 8 weeks of non-missing diary data and who did not withdraw early from study.
- Best Case Scenario: Assume all subjects with missing data in study group are successes; Assume all subjects in the placebo group with missing data are failures.
- Worst Case Scenario: Assume all subjects with missing data in study group are failures; Assume all subjects in the placebo group with missing data are successes.

In addition, for missing diary day, the number of bowel movement will be imputed to "0", and the intake of rescue medicine to "No". For the time to first SBM analysis, subjects with no known SBM will be considered left censored.

For the analyses of the other endpoints, no imputations for missing values will be performed.

Doc No: 280CLD

Rev: 01 Date: 24 May 2021

Page 75 of 103

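### Primary (mITT) analysis: the evaluability rule in 17.8.3 takes early stoppers out of the denominator, where the missing-data rule in 17.9.8 would count them as failures

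*Combined protocol and SAP*

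**What the plan says.** Section 17.8.3 defines mITT as randomized subjects who met the inclusion criteria. It adds that those with "less than 2 weeks (with at least 5 days per week) of valid diary during the treatment period will be considered as non-evaluable", without saying what follows from that label. Section 17.8.5: "The mITT analysis set will serve as the main set for efficacy assessments".

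Section 17.9.8 gives the primary imputation method: "Subjects with less than 6 weeks of diary data will be considered as failures for the CSBM and SBM success rates". It sets no lower bound, names no analysis set, does not refer to 17.8.3 and does not define a diary week. It adds that "for missing diary day, the number of bowel movement will be imputed to" zero. It also promises that "Additional sensitivity analysis of the primary end-point will be performed to assess the impact of missing data on the study outcome", by multiple imputation and by observed-data, best-case and worst-case analyses.

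Both the ITT and the mITT definitions carry a further exclusion: "Subjects with no valid post baseline assessment will not be part of the relevant analysis". The 2-week rule stands only under mITT.

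For the interim, 17.5.1 says "At the interim analysis, the data of the evaluable subjects will be analyzed", while 17.5.3 says that the "interim analysis will be conducted on both the ITT and mITT analysis sets".

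**The concern.** A subject with 0 or 1 valid week and some diary data falls under both rules. If non-evaluable means removed, randomized subjects leave the primary comparison because of something that happened after randomization. Two kinds of subject are affected:

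- **Early stoppers.** They cannot meet 6 of 8 weeks. Removing them removes known failures and raises the observed success rate of their arm.
- **Sparse diary-keepers.** A subject with 4 entries in each of 8 weeks has no valid week under the 5-day rule. Missing days count as zero bowel movements, so the criterion could still be met. This subject is not a certain failure.

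What is at stake is the denominator of both primary endpoints, and with it the interim conditional power. The choice should be settled before anyone sees data by arm.

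**Working it through.** **Inputs from the documents.** Success 12% placebo and 40% active (12% + 28%), two-sided 2.5% per primary endpoint, 46 per arm, 51 per arm with 10% drop-out (17.4); success means at least 6 of 8 weeks (17.2.1). **Assumed:** early loss by arm and the outcome of those lost, since the documents give only the overall 10%.

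**The plan's own figure.** Power = Φ{[|p1 − p0|√n − 2.2414·√(2p̄q̄)] / √(p1q1 + p0q0)}. With n = 46: (0.28 × 6.782 − 2.2414 × 0.6203) / 0.5879 = 0.865, so power is 80.7%. The stated 92 subjects reproduce, and the sample size is not in dispute.

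**Why deletion shifts the rates.** Let the success rate among all randomized be p in both arms, and let a share d be lost, all failures. After deletion the expected rate is p/(1 − d). At p = 20% with 8% active and 2% placebo loss this is 21.7% v 20.4%; at 5% v 5% it is 21.1% in both arms.

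**False-positive rate in favor of the device** (nominal 1.25%). Simulation of a Cochran-Mantel-Haenszel (CMH) test with one stratum, 51 per arm, all lost subjects failures:

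| Success rate, both arms | Loss, active v placebo | Deleted | Scored as failures |
|---|---|---|---|
| 12% | 8% v 2% | 1.6% | 1.1% |
| 12% | 10% v 0% | 2.0% | 1.1% |
| 20% | 5% v 5% | 1.2% | 1.2% |
| 20% | 4% v 2% | 1.4% | 1.2% |
| 20% | 8% v 2% | 1.8% | 1.2% |
| 20% | 10% v 0% | 2.4% | 1.2% |
| 20% | 0% v 10% | 0.6% | 1.2% |

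Stratifying by center as planned (102 subjects over 30 centers, assumed blocks of 2 or 4) gives slightly smaller figures at 20%: deletion 1.7% at 8% v 2% and 2.2% at 10% v 0%.

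**If the lost subjects are not failures.** At a 20% success rate, if 20% of those lost would also have met the criterion, deletion stays at about 1.2% in every loss pattern. Failure scoring then gives 0.6% at 10% v 0% and 2.3% at 0% v 10%.

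**How many subjects it takes.** χ² = (a − n1t/N)² / [n1n0t(N − t) / (N²(N − 1))], where a is active successes and t is all successes, judged at 2.5% (the Benjamini-Hochberg level when the other primary p-value exceeds 5%):

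- 16/51 v 7/51: (16 − 11.5)²/4.4975 = 4.50, p = 0.034. Two active deletions (16/49) give p = 0.0253, not significant; three (16/48) give p = 0.0216, significant.
- 17/51 v 7/51: p = 0.0202. Two placebo deletions (7/49) give p = 0.0265, and significance is lost.
- Two deletions in each arm (16/49 v 7/49): p = 0.033, no change.

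**Diary-week definition.** With independent daily completion of 80% to 95% (assumed), the share of subjects with under 6 diary weeks runs from 10.2% down to about 0% if a week needs 5 days, and from 99.8% down to 45.2% if it needs all 7.

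**The case against.** A reader might infer that the two sections contradict each other. They need not. One rule sits with the analysis sets and the other is an imputation method; defining the set and then imputing within it is the ordinary order, and it leaves no conflict. What remains is a denominator that depends on post-randomization behavior, an undefined consequence of being non-evaluable, and an undefined diary week.

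A reader might also infer that deletion favors the device. The documents do not support this. They give no early loss by arm, and deletion favors the device only if the active arm loses more and those lost are mostly failures. The 10% drop-out figure covers the whole study, so 8% v 2% and 10% v 0% are strong assumptions: they put half of all drop-out in the under-2-week group and most or all of that in one arm.

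The plan already offsets much of this. ITT has no 2-week rule, so the supportive ITT analysis largely shows the failure-scored result, except for subjects with no valid post-baseline assessment. Futility stopping requires both ITT and mITT to fall below the threshold. The 17.9.8 sensitivity analyses help too, but no set is named for them; run within mITT, they would omit the subjects at issue.

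Finally, failure scoring is not free of bias. Its 2.3% for unbalanced sparse diary-keepers is close to the 2.4% worst case for deletion. That stands, and it is why the evaluable-only analysis should be kept.

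**Conclusion.** The point holds as a correction worth making before unblinding, not as a flaw that decides the trial. Under the natural reading, the main efficacy analysis drops randomized subjects on post-randomization diary completion, including early stoppers who are failures by definition. The effect is nil or small when loss is balanced or when those lost would have succeeded like everyone else. Under marked imbalance with all lost subjects failing, the device-favoring error rises from about 1.1–1.2% to 1.6–2.4%, or falls to 0.6% when the imbalance is reversed. These figures rest on assumed loss and on one endpoint tested at 2.5%. Two or three subjects can move a borderline result, in either direction.

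**What to change.** For the CSBM success endpoints in the primary mITT analysis:

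1. Keep every randomized subject who met the inclusion criteria. Delete the under-2-week and no-post-baseline exclusions.
2. Score subjects with under 6 diary weeks, including none, as failures.
3. Use one definition of a valid diary week in 17.8.3 and 17.9.8, for example the existing 5-day rule.
4. At the interim, apply this only to subjects who have completed 8 weeks, have exited, or whose 8-week window has closed. Subjects still on treatment must not be counted as failures for weeks not yet reached.
5. Keep the evaluable-only analysis as a sensitivity analysis, and run the 17.9.8 sensitivity analyses on all eligible randomized subjects.

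The cost is wording plus a restated power. If all of the 10% drop-outs are failures, the rates become 36.0% (0.9 × 40%) and 10.8% (0.9 × 12%), and power at 51 per arm is 78.8%. At 5% drop-out (38.0% v 11.4%) it is 82.1%. Failure scoring can bias the comparison if sparse diary-keepers are unbalanced and would have succeeded, and the 5-day rule makes some of them failures. The evaluable-only and multiple-imputation analyses show how far that matters.

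A separate correction, for an additional endpoint only: 17.9.8 treats subjects with no known SBM as left censored in the time-to-first-SBM analysis. The planned Kaplan-Meier and log-rank methods need them right censored, at the last completed diary day.

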17.8.4 Per-Protocol (PP)

The per-protocol analysis set will consist of all subjects from the mITT analysis set without major protocol violations and successfully completed the study, with treatment group analyzed as treated.

17.8.5 Statistical Analysis of Analysis Sets

The SA analysis set will serve as the main set for safety assessments.

The mITT analysis set will serve as the main set for efficacy assessments.

The efficacy assessment will be presented on the ITT and PP analysis sets.

17.9 Statistical Analysis

17.9.1 General Considerations

Statistical analyses will be performed using SAS® v9.4 or higher (SAS Institute, Cary NC, USA).

Baseline demographic and other baseline characteristics, together with safety analyses will be performed on all enrolled subjects.

Baseline values are defined as the last valid value prior to treatment.

All statistical tests will be two-sided. If statistical tests are performed nominal p-values will be presented. Where confidence limits are appropriate, non-adjusted two-sided 95% confidence interval will be constructed.

For comparison of means (continuous variables), the two-sample t-test or the Wilcoxon rank sum test will be used as appropriate. For comparison of proportions (categorical variables), the Chi-squared test or Fisher's exact test will be used as appropriate.

17.9.2 Significance levels and handling of type I error

17.9.2.1 Type I Error

The overall significance level for this study is 5% using two-tailed tests. According to references 25-27, planning an interim analysis that permits an increase in the sample size as described in section 17.5 does not inflate the type I error. The treatment by site interaction will be tested at a significance level of 10%.

17.9.2.2 Primary Endpoints

The Benjamini Hochberg procedure for controlling the false discovery rate will be implanted for the two primary endpoints.

17.9.2.3 Hierarchy Approach for Secondary Endpoints Analysis

The hierarchy approach will be adopted for the primary and secondary endpoints to control type I error due to multiple endpoints testing. Thus, the primary endpoint will first be analyzed and only if at least one of them is found statistically significant, will the secondary endpoints be analyzed.

The first secondary endpoint will be tested, first, for statistical significance and only if found significant (versus an alpha level of 5% if both primary endpoints are found statistically significant, or 2.5% if only one of the two primary endpoints is found statistically significant), the next in line will be tested. Only if the first and second secondary endpoints are found statistically significant, then the third one will be tested, and so on.

The order of the secondary endpoints is as listed in paragraph 17.2.2.

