17.2 Study Endpoints

17.2.1 Primary Efficacy Endpoint

There are two primary efficacy endpoints for this study.

The two primary efficacy endpoints are the CSBM1 success rate, defined as an increase from the run-in period of at least one weekly Complete Spontaneous Bowel Movement (CSBM) during at least 6 of the 8 weeks of treatment, and CSBM2 success rate, defined as an increase from the run-in period of at least two weekly Complete Spontaneous Bowel Movement (CSBM) during at least 6 of the 8 weeks of treatment.

The study will be deemed successful if either the CSBM1 or the CSBM2 success rate is statistically significantly higher in the active arm, than in the placebo arm.

Doc No: 280CLD Rev: 01 Date: 24 May 2021

Page 66 of 103

17.2.2 **Secondary Efficacy Endpoints**

Secondary efficacy endpoints include:

- Change from baseline in average straining. 1.
- 2. CSBM1 expanded success rate, defined as an increase from the run-in period of at least one weekly Complete Spontaneous Bowel Movement (CSBM) during at least 5 of the 8 weeks of treatment.
- Change from baseline in average stool consistency, using the Bristol Stool Scale 3.
- 4. CSBM2 expanded success rate, defined as an increase from the run-in period of at least two weekly Complete Spontaneous Bowel Movement (CSBM) during at least 5 of the 8 weeks of treatment
- 5. Change from baseline in average bloating.

17.2.3 **Additional Efficacy Endpoints**

Additional efficacy endpoints include:

- SBM success rate, defined as an increase from baseline at least one weekly spontanuous Bowel Movement (SBM) during at lease 6 out of 8 weeks of treatment.
- Incidence of Rescue Medication use during the treatment period.
- Change from baseline in weekly number of Spontaneous Bowel Movement (SBM).
- Change from baseline in weekly number of Complete Spontaneous Bowel Movement (CSBM).
- Rate of SBM < 24 hours after first dose
- Change from baseline in average abdominal gas.
- Change from baseline in average abdominal pain.
- Change from baseline in abdominal discomfort.
- Time to occurrence of spontaneous bowel movement after first capsule activation.
- Change from baseline in quality of life using the PAC-QOL (Patient Assessment of Constipation Quality of Life) questionnaire.

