17.4 Sample size

A sample size is calculated to test the null hypotheses. Calculations (using SAS® proc power) show that a sample size of 92 subjects (46 in each study arm), would provide 80% power at a study wise 5% level of significance (two-sided), i.e., 2.5% for each one of the primary endpoints to detect a difference of 28% in the success rate, assuming a success rate of 12% in the placebo arm.

The sample size will be increased to at least 102 subjects (51 in each study arm) to account for a potential 10% of drop-out rate.

Doc No: 280CLD

Rev: 01 Date: 24 May 2021

Page 68 of 103

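### If Benjamini-Hochberg is run at 5%, nothing covers the 2.5% that the plan passes to the secondary endpoints after a win on only one primary

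*Combined protocol and SAP*

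**What the plan says.** Four places in section 17 bear on this.

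- Section 17.9.2.1: "The overall significance level for this study is 5% using two-tailed tests".
- Section 17.9.2.2: "The Benjamini Hochberg procedure for controlling the false discovery rate will be implanted for the two primary endpoints". No level is given.
- Section 17.9.2.3: "The hierarchy approach will be adopted for the primary and secondary endpoints to control type I error due to multiple endpoints testing". The secondaries open once at least one primary is significant. They are then tested in fixed order, starting with straining, "versus an alpha level of 5% if both primary endpoints are found statistically significant, or 2.5% if only one of the two primary endpoints" is significant.
- Section 17.4: "a sample size of 92 subjects (46 in each study arm), would provide 80% power at a study wise 5% level of significance", read there as "2.5% for each one of the primary endpoints to detect a difference of 28% in the success rate", with a placebo rate of 12%.

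Under section 17.2.1 the study succeeds if either primary is significant, so a one-primary win is an outcome the plan provides for.

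**The concern.** With two endpoints, Benjamini-Hochberg at 5% rejects both nulls if the larger p-value is at most 5%. Otherwise it rejects the one with the smaller p-value if that is at most 2.5%. Once one primary is clearly significant, the other is therefore tested at the full 5%. If it fails, the whole 5% has been spent on it, yet section 17.9.2.3 gives the secondaries a further 2.5%.

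That release belongs to a split-alpha scheme in which each primary has its own 2.5% and a winner passes its share on. It does not fit Benjamini-Hochberg at 5%. What is at stake is the stated type I error control for secondary claims made after exactly one primary wins. The 2.5% sizing in section 17.4 is not itself in conflict, because Benjamini-Hochberg at 5% compares the smaller p-value with 2.5%.

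**Working it through.** **Inputs.** From section 17.4: 12% versus 40% (12% + 28 points), 46 per arm, 80% power, two-sided 2.5% per primary. From sections 17.9.2.1 to 17.9.2.3: overall 5%, Benjamini-Hochberg, and the 5%/2.5% release. Correlations between test statistics are not in the documents and are assumed.

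**The plan's sample size.** With pooled variance and mean rate 0.26, n per arm = [2.2414·√(2·0.26·0.74) + 0.8416·√(0.40·0.60 + 0.12·0.88)]² / 0.28² = (1.390 + 0.495)² / 0.0784 ≈ 45.3, so 46 per arm and 92 in total. This agrees with section 17.4; power at 46 per arm is 80.7%.

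**Bound.** Take one primary effective, and the other primary and the first secondary null. With Benjamini-Hochberg at level q, the error is at most q + 2.5%. That is 7.5% at q = 5% and 5.0% at q = 2.5%.

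**Independent statistics, planned power.** The effective primary has mean 2.2414 + 0.8416 = 3.083. It reaches p ≤ 2.5% with probability 0.80 and p ≤ 5% with probability 0.869.

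- Effective primary at p ≤ 2.5% (0.80): the null primary is falsely rejected at 5%; if it is not, the secondary is tested at 2.5%. Error 0.05 + 0.95 × 0.025 = 0.07375.
- Effective primary between 2.5% and 5% (0.069): an error needs the null primary at p ≤ 5%. Error 0.05.
- Effective primary above 5% (0.131): an error needs the null primary at p ≤ 2.5%. Error 0.025.

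Total: 0.80 × 0.07375 + 0.069 × 0.05 + 0.131 × 0.025 = 0.0657, or 6.6%. As power nears 100% it tends to 7.4%.

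**Correlated statistics** (trivariate normal simulation, 4 million draws, common correlation):

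| Correlation | 0 | 0.3 | 0.5 | 0.7 | 0.8 | 0.9 |
|---|---|---|---|---|---|---|
| 80% power | 6.6% | 6.2% | 5.7% | 5.0% | 4.6% | 4.1% |
| 90% power | 7.0% | 6.7% | 6.2% | 5.4% | 4.9% | 4.4% |
| Power near 100% | 7.4% | 7.2% | 6.9% | 6.5% | 6.1% | 5.6% |
| All three null | 5.0% | 4.9% | 4.8% | 4.6% | 4.4% | 4.2% |

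At 80% power, if only the primaries are highly correlated (0.8-0.9), the error is 5.2-5.7% with the secondary at 0.3-0.5 and 4.7-4.8% with it at 0.7.

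**How correlated can the primaries be?** CSBM2 success implies CSBM1 success. If CSBM1 is 12% versus 40% and CSBM2 is null at rate p, then p is at most 12%. The correlation of the two rate differences is (0.60p + 0.88p) / √[(0.24 + 0.1056)·2p(1 − p)], which is 0.41 at p = 5% and 0.66 at 12%. The pooled chi-square statistics simulate at 0.44 and 0.71.

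**Nested binary simulation** (46 per arm, Pearson chi-square with the (N − 1)/N factor, t-test for straining, 300,000-400,000 trials per cell):

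| CSBM2 rate | Patient-level correlation with straining 0 | 0.5 | 0.7 |
|---|---|---|---|
| 1% | 2.1% | 1.9% | 1.8% |
| 3% | 4.1% | 3.9% | 3.7% |
| 4% | 5.1% | 4.8% | 4.6% |
| 5% | 5.7% | 5.3% | 5.2% |
| 8% | 5.9% | 5.6% | 5.4% |
| 12% | 6.0% | 5.7% | 5.5% |

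The reverse case (CSBM2 12% versus 40%, CSBM1 null at 40-60%) gives 5.2-6.2%. A separate nested simulation without the (N − 1)/N factor gave 5.8-6.9% for CSBM2 rates of 5-12%.

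**Other rules, same scenarios.** The largest error is 4.9% with each primary at a fixed 2.5% and the release kept, 4.9% with Benjamini-Hochberg at 2.5%, and 5.0% with Benjamini-Hochberg at 5% and secondaries only after two wins.

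**The case against.** The strongest reply is that the fault depends on a reading. Sections 17.4 and 17.9.2.3 both speak of 2.5% per primary and are valid together; the leak appears only when section 17.9.2.2 is run at 5%. That is so, but the plan states an overall 5% and no other level for the procedure, so control depends on something the plan leaves out.

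Second, the generic range straddles 5%, and its upper end needs independence that nested endpoints cannot have. This stands. The plan-specific figures are the fairer guide, and they show no excess at low CSBM2 rates.

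Third, section 17.9.5 specifies a Cochran-Mantel-Haenszel test controlling for center and ANCOVA with site, in about 30 centers, not unstratified tests. A rerun with center-stratified tests (92 subjects spread at random over 30 centers, no baseline straining covariate, 75,000 trials per cell) gave 3.3-3.8% at a CSBM2 rate of 3%, 4.8-5.2% at 5%, 5.3-6.0% at 8% and 5.3-5.8% at 12%. The excess becomes smaller but remains.

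Fourth, the scenario is narrow: a large effect on one CSBM threshold, and none on the other or on straining. That limits the importance of the point, but control of type I error has to cover this scenario too.

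**Conclusion.** The concern holds. With Benjamini-Hochberg at the overall 5%, the hierarchy does not have the type I error control that section 17.9.2.3 claims. The bound is 7.5%. With the plan's rates and nested endpoints, the error is about 5-6% for CSBM2 rates of 5-12%, with no excess at 1-3%.

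The logic is certain; the size is less so. It rests on assumed correlations, on an assumed null CSBM2 rate, and on which primary the 12% and 28 points in section 17.4 describe. The interim adaptation is not modelled. An increase towards the 250 maximum in section 17.5.3 would raise power and could raise the error: a fixed-size illustration at 125 per arm gives 6.7-7.4%.

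Only secondary claims after a one-primary win are exposed. The primary success claim is unaffected, there is no excess when all three endpoints are null, and Benjamini-Hochberg at 2.5% would keep the total within 5.0%.

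**What to change.** Before unblinding, state the level for the primaries and make sections 17.9.2.2 and 17.9.2.3 one consistent rule. Only SAP text changes.

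- **Preferred:** test each primary at a fixed two-sided 2.5%, the level already used in section 17.4, and keep the 5%/2.5% release. With one null primary, the error is at most 2.5% on that primary plus 2.5% on the secondaries, so at most 5%. The 92-subject basis does not change. What is lost is the case where both p-values lie between 2.5% and 5%. At a correlation of 0.65 between primaries, study success goes from 90.3% to 89.4% when both have 80% power, and from 74.8% to 73.3% when both have 60%. Over correlations of 0.3-0.8 the loss is 0.1-1.9 points.
- **Alternative:** keep Benjamini-Hochberg at a stated 5% and open the secondaries only when both primaries are significant. This gives up confirmatory secondary claims after a one-primary win. With the first primary at 80% power and correlation 0.3-0.8, exactly one primary wins in 6.7-16.8% of trials if the second also has 80% power, 14.5-25.9% if it has 60%, 30.1-38.6% if it has 40%, and 76.7-78.5% if it is null.

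Benjamini-Hochberg at a stated 2.5% with the release kept is also valid. However, a lone winner would then need p ≤ 1.25% (2.5%/2), which is stricter than the level used for sizing in section 17.4.
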